11.3 Loss to follow up

The directness of the telephone approach and short duration of follow-up (8 weeks after birth of the baby) mean that the risk of loss to follow-up is lower than in studies with longer follow-up. The use of routinely collected NHS data (if feasible) should provide data on breastfeeding maintenance with minimal loss to follow-up.

12 Intervention

12.1 Intervention arms

There will only be one arm in this feasibility study.

Peer supporter training and on-going support

Prior to recruiting the first participant, breastfeeding peer supporters and midwife supervisors taking part in this study will receive additional training. The training will aim to provide peer-supporters with a uniform framework that allows flexibility to be responsive to event triggers (e.g. night feeds, change from colostrum to milk) and motivational interviewing techniques that will enable them to raise the necessary topics in a forum where discussion is balanced against the mother's concerns, needs and goals. Each visit by the peer-supporter will be characterised by rapid engagement skills, skilful information exchange (a toolkit will be developed as part of the intervention to facilitate this) and goal setting.

Informed by the qualitative work with peer-supporters (Objective 2), we anticipate providing approximately 16 sessions of additional face-to-face training covering the core elements of BFPS and the MI-based approach, accompanied by completion of a reflective practice portfolio, formal MI supervision sessions, and on-going supervision and support from the community midwifery team as described below.

[name] will be responsible for the overall development of the MI based BFPS training course. This will be informed by the work that has already been done in Bristol on training peer-supporters and further developed in consultation with our stakeholder advisory group, with representation from peer-supporters, midwives, health visitors, pregnant women and mothers. The training course will have three modules: (i) core elements of breastfeeding peer-support (BFPS), (ii) using a motivational interviewing (MI) approach and (iii) safe and effective practice.

[name] will lead on establishing the model for training in using an MI based approach (not MI counselling in its original form which would require far more time and training to become skilled in). This will be based on an existing core-training package, adapted to be suitable for delivery by peer supporters, and on-going MI coaching sessions, in line with the emerging evidence on the effectiveness of training in MI. The baseline training and on-going coaching will be provided as specified by MI trainers who are members of the Motivational Interviewing Network of Trainers (MINT). [name] will provide training on the core elements of breastfeeding. [name] and the community midwife we will recruit to the research team will provide training on safe and effective practice, including issues around safety, roles, boundaries, communication, referral and care pathways, reporting of significant events and support systems in place.

The full MI based BFPS training package (all three modules) will consist of 16 sessions (total 64 hours). The MI module will consist of 16 hours (delivered over two days), to include basic training in using the MI approach, followed by role-plays, protocol specific practice and feedback on performance. The other two modules will be covered in the remaining 48 hours of training. Having completed training, peer-supporters will receive MI coaching every two weeks by the same trainer with a focus on improving peer-supporters engagement skills and ability to elicit solutions from the mothers they support. We have modelled this approach based on the work by Naar-King and colleagues who have shown that peer youth workers can be trained to use an MI based approach (11).

Peer-supporters will be expected to have (i) already completed breastfeeding peer-support training accredited at Level 1 by awarding organisations (e.g. Agored Cymru) to ensure a good understanding of current advice on breastfeeding and a sufficient level of literacy, (ii) the necessary personal attributes (warmth, likeable, discreet, aood communication skills and ability to listen), and (iii) be able to work within quidelines. Following training in using the MI approach, peer- supporters will be required to achieve fidelity scores indicating at least beginner level competency (using the MITI assessment tool) before they start their practice.

A named midwife at each site will be responsible for the overall supervision of the peer-supporters working in their area. The midwife will maintain regular contact with the peer-supporters (at least once a week) and be the point of contact to discuss any clinical aspects, referrals, concerns or issues that may arise in the interaction between peersupporters and the mothers that they support. We will provide the community midwives who will supervise peer-supporters with the same training in using an MI approach that is provided to peer-supporters, to ensure acceptance of MI principles and consistency of messages that are used.

Following each interaction (face-to-face, telephone, online or text message), the peer supporter will record brief details in a structured diary. Adherence to data collection will be monitored through supervision by community midwives and cross-referencing with peer supporters' work telephone records. Peer supporter diaries will also be used as a tool for

discussing support needs and ensuring established protocols for referring women for medical support are working as expected.

Each visit by the peer-supporter will be characterised by rapid engagement skills, skilful information exchange (a toolkit will be developed as part of the intervention to facilitate this) and goal setting. Informed by the qualitative work with peer-supporters (Objective 2), we anticipate providing approximately 16 sessions of additional face-to-face training covering the core elements of BFPS and the MI-based approach, accompanied by completion of a reflective practice portfolio, formal MI supervision sessions, and on-going supervision and support from the community midwifery team as described below.

Intervention

Women who are considering breastfeeding will be provided with the opportunity to receive breastfeeding support from a trained peer supporter. Participants will receive at least one antenatal contact, and contact within 48 hours of birth. It is anticipated that support will be most intense within two weeks of birth. The full content and specification of this will be defined during the development phase (objectives 1-3), and this protocol will be updated. For example, we will consider using a 24hour telephone number for the delivering midwife to leave a message at any time; stickers on the woman's maternity notes with the individual peer supporter's name and phone number, to be rung and message left either by the woman, partner or midwife shortly after the birth.

13 Adverse Events

Adverse Event (AE): Any untoward medical occurrence in a study participant which does not necessarily have a causal relationship with this treatment. An AE can therefore be any unfavourable and unintended sign (including abnormal laboratory finding), symptom, or disease.

Serious Adverse Event (SAE): Any adverse event, affecting either the mother or baby, that:

- Results in death
- Is life-threatening*
- Required hospitalisation or prolongation of existing hospitalisation (for reasons other than the birth of the baby)**

- Results in persistent or significant disability or incapacity
- Consists of a congenital anomaly or birth defect
- Other medically important condition ***

* Note: The term "life-threatening" in the definition of serious refers to an event in which the participant was at risk of death at the time of the event; it does not refer to an event which hypothetically might have caused death if it were more severe.

** Note: Hospitalisation is defined as an inpatient admission, regardless of the length of stay, even if the hospitalisation is a precautionary measure, for continued observation. Pre-planned hospitalisation e.g. for the birth of the baby or pre-existing conditions which have not worsened or elective procedures does not constitute an adverse event.

*** Note: other events that may not result in death are not lifethreatening, or do not require hospitalisation may be considered as a serious adverse event when, based upon appropriate medical judgement, the event may jeopardise the participant and may require medical or surgical intervention to prevent one of the outcomes listed above.

13.1 Causality

The assignment of the causality should be made by the Investigator responsible for the care of the participant using the definitions in the table below.

If any doubt about the causality exists, the local Investigator should inform the Peer support for breastfeeding maintenance study manager who will notify the Chief Investigator.

In the case of discrepant views on causality between the site and the clinical reviewer, the event will be handled at the highest event categorisation.

Relationship	Description
Unrelated	There is no evidence of any causal relationship with the trial/study or intervention
Unlikely	There is little evidence to suggest there is a casual relationship (e.g. the event did not occur within a reasonable time after intervention) with the study/trial or intervention. There is another reasonable explanation for the event (e.g. the participant's clinical condition, other treatment).
Possible	There is some evidence to suggest a causal relationship with the trial/study or intervention (e.g. because the event occurs within a reasonable time after intervention). However, the influence of other factors may have contributed to the event (e.g. the participant's clinical condition, other treatments).
Probable	There is evidence to suggest a causal relationship and the influence of other factors is unlikely.
Definite	There is clear evidence to suggest a causal relationship and other possible contributing factors can be ruled out.
Not assessable	There is insufficient or incomplete evidence to make a judgement of the causal relationship.

13.2 Reporting procedures

Depending on the nature of the event, the reporting procedures outlined in this protocol should be followed. Any queries concerning adverse event reporting should be directed to the study manager in the first instance.

SAEs

Contact the study coordination centre by phone and then send the completed SAE form to the study coordination centre within the following 24 hours as above.

All SAE forms will be reviewed by a clinician to ensure appropriate action. Although the intervention is being delivered in the late antenatal period and unlikely to be related to the development of congenital anomalies these will be reported to the study team to ensure they are aware before contact is made.

14 Study procedures

14.1 Data collection

- (i) A baseline questionnaire will be completed by the researcher at the initial appointment (30 – 34 weeks gestation) covering sociodemographic variables, infant feeding intentions (45), prenatal attachment (46), maternal health and well-being.
- (ii) A follow-up telephone interview will be carried out by the researcher at 8 – 10 weeks after birth to ascertain duration of exclusive or partial breastfeeding, breastfeeding attitudes, use of usual care BF support (healthcare professionals, BF groups), maternal and child health and well-being.
- (iii) We will look at how we can facilitate health visitors to capture the data on some outcome measures (exclusive and partial breastfeeding at 8 weeks, maternal and child health and well-being)

at source and make it available to the research team. The research team has relevant experience from the Building Blocks Trial of developing methods to collect outcome data using both telephone interviews and routinely collected data by Health Visitors, which was underpinned by theory and strategically addressed organisational and motivational aspects within the research and clinical teams (44).

- (iv) We will investigate the availability and potential for using routinely collected data on Child Health Systems, General Practice databases and Hospital Episode Statistics to capture data on infections, hospital admissions and contact with accident and emergency and primary care services.
- (v) Semi-structured interviews with a subset of participants (n=30), peer-supporters (n=6-9) and healthcare professionals (n=9) will be carried to assess the acceptability and feasibility of delivering MI based BFPS including intervention fidelity as part of a process evaluation.
- (vi) Audio recording of a selection of peer supporter-mother interactions to assess fidelity to MI principles.

The research management team ([name], [name], [name], [name], [name]) will be responsible for the strategy to ensure adherence to data collection and the researcher will take responsibility for its implementation. The research management team will monitor the quality of data collection through regular surveillance tailored to the data collection schedule, for quality (including response rates, frequency of data returns, completeness and accuracy) and develop specific follow-up tasks to address any issues.

Quantitative data items to be collected are described in Appendix 2.

14.2 **Process evaluation**

We will evaluate what processes influence MI based BFPS outcomes in order to explore applicability to other settings and to optimise its implementation (47). Specifically, we will examine intervention exposure, participants' engagement and satisfaction with MI based BFPS, wider contextual influences on MI based BFPS implementation and outcomes, and acceptability of research processes including method of identifying participants, referral to the research team and peer-supporter, and study materials.

Around ten mothers in each of the three sites will take part in a face-toface interview (n=30). We will recruit a purposive sample, based on site, peer supporter delivering the service, success at breastfeeding at 10 days and 6-8 weeks and level of engagement with the intervention. We will aim for a sample in which at least half will be under 20 years of age. In order to compensate women for their time we will provide a high street voucher on completion of the interview. We will interview all peer supporters delivering the intervention (n=6-9). We will also purposively sample health professionals who have had active engagement in the study and interview one midwife, one health visitor and one service manager from each area in which the intervention is hosted (n=9).

Participants will take part in a semi-structured interview, based around their experiences and views of the intervention. A topic guide will be constructed for each group of participants, to retain a focus on the intervention (68). Key topics will include mothers' thoughts on having intensive breastfeeding peer-support; peer supporters' training and supervision; and the views of health professionals on how well the intervention fits alongside existing services. Mothers and peer supporters will be interviewed in a venue of their choice, to minimise drop out. Cardiff University safeguarding procedures will be followed when conducting research in participants' homes. Health professionals will be interviewed either face-to-face at their workplace or by telephone as this has been shown to be useful in securing participation in qualitative research from busy professionals (75).

Peer supporters will complete structured diaries following each interaction with a participant. The design of the diaries will be informed by the qualitative work with peer-supporters in Objective 2 but it is likely that the diaries will be no more than a page for each interaction, with tickboxes for the mode of interaction (eg: text message, telephone, face-toface), length of interaction and travel time, and content domain coverage to assess fidelity. In addition, diaries will be used in supervision sessions to identify support needs, as is used in other peer supporter interventions (76).

14.3 Fidelity assessment:

We have evidence that the effectiveness of MI based interventions can be related to low quality MI being delivered (57). Peer supporters will audio-record interactions between themselves and study participants in order to

ensure fidelity to MI principles and quality of breastfeeding advice provided. During the development stage (Objective 2), we will ascertain whether it is acceptable to record all interactions and then analyse a random sample, or if only interactions that are going to be analysed should be recorded. All peer supporters will record a selection of their interactions, and these may be face-to-face or by telephone depending on the route in which support is most often provided by individual peer supporters. The peer supporters will be responsible for obtaining consent to audio record interactions prior to recording an interaction. We will analyse the recording of three interactions per peer supporter, covering one interaction within 48 hours after birth and two thereafter. Audio recordings will be assessed for content domain coverage and MI competencies as described in the data analysis section on page 16.

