Intervention: MI based BFPS, characterised by proactive daily one-toone peer-supporter led contact for at least 2 weeks, initiated within 48 hours of birth. Peer-supporters are women from a similar locality to the women they support, who have breastfed, completed accredited BFPS training and MI training. Content, optimal timing and methods of contact, training of peer-supporters, and implementation alongside existing services will be informed by focus groups with pregnant women, mothers, fathers and peer-supporters, interviews with midwives, health visitors and service managers.

Measurement of costs and outcomes: Quantitative data will describe BFPS uptake, completion of scheduled contacts with peer-supporters according to age-group and parity; recruitment and retention of peersupporters; and intervention costs from the perspective of the UK NHS, women and their families. Feasibility of different methods (structured telephone interviews with all mothers, data collected by Health Visitors and routine NHS data from Child Health Systems, Hospital Episode Statistics and General Practice) will be assessed to collect outcome data (exclusive and partial BF maintenance at 10 days and 6-8 weeks, maternal and child health, well-being, satisfaction and healthcare resource utilisation). Peer-supporter structured diaries, audio recorded peer supporter-mother contacts (n=27) and qualitative interviews with mothers (n=30, at least half aged <20), peer-supporters (n=6-9) and health professionals (n=9) to assess acceptability, intervention fidelity and feasibility of providing MI based BFPS to the target population.

Analysis: Quantitative data will be described using percentages and 95% confidence intervals (categorical data), and mean, standard deviation and 95% confidence intervals (continuous data). Thus summary data for the whole group and by site will provide information relevant to inform a full trial. The inter-class correlation will be estimated from the site data regarding variation in breast feeding outcome using ANOVA. Audio recordings will be analysed using the Motivational Interviewing Treatment Integrity (MITI) code (1, 2) and content domain analysis. Qualitative data will be input into NVivo 10 and analysed using framework analysis, allowing for inductive and deductive coding (3).

4 Introduction

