10.2 Recruitment process

Qualitative development work

For the qualitative development work we will recruit parents from existing parenting groups in each of the three research sites, facilitated by local collaborators ([name], [name], [name]). Peer supporters will be recruited by local managers from existing databases of peer supporters, co-ordinated by [name] and [name]. Health professionals and managers will be recruited using existing networks of study co-applicants and collaborators.

Recruitment of peer supporters for feasibility study:

We will recruit 6-9 peer supporters (2-3 in each of the study sites) who have completed accredited BFPS training. We will use a formal advertisement and interview process in order to recruit from the existing database of peer-supporters in the three study areas. We will access these peer-supporters through midwifery and health visiting staff who support volunteers and maintain local databases of peer supporters (approximately 40 peer supporters per area), local breastfeeding groups, supervision and update sessions (where these are available) and from local Facebook sites where they are freely accessible in the public domain. Additional ways of disseminating the advertisement may be included following the focus groups with peer supporters in objective 2.

Recruitment of local study midwives for feasibility study:

We will recruit one practicing midwife in each site to provide support to peer supporters delivering the feasibility study intervention. [name], [name] and [name] will request expressions of interest for the role, in collaboration with heads of midwifery.

Recruitment of feasibility study participants

Potential participants (n=800) will be identified in conjunction with staff from maternity teams providing antenatal care in the study areas. Midwives will introduce the study to pregnant women at around 28 weeks gestation and obtain agreement to forward the potential participants' contact details to the research team. Women who participated in the qualitative development work will be excluded from this element of the study.

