15.2 Sample size

This feasibility study is not powered to detect statistical significance.

16 Analysis

Objective 1

Descriptive statistics will be used to show the current range of UK BFPS using data generated from the web-based survey of service providers. A narrative synthesis will be used to critique and summarise the characteristics of UK BFPS and any underpinning theoretical models.

Objective 2

Focus groups and interviews will be audio recorded and transcribed verbatim. Transcripts will be input into NVivo 10, and will be analysed using framework analysis (87) based on concepts within the Behaviour Change Wheel framework (9). This will allow the data to be analysed in a

structured way which is particularly helpful during intervention development and evaluation. The coding framework will include the items on the topic guide, as well as additional codes including barriers and facilitators to implementing and using the intervention. A random sample of 30% of transcripts will be coded by a second researcher, and any inconsistencies will be discussed and resolved.

Objective 3

We will map the theoretical models identified in the evidence review (objective 1) and the results from the qualitative work (objective 2) against the Behaviour Change Wheel framework (9) to specify the relevant sources of behaviour and corresponding intervention functions, and develop a logic model for the intervention.

Objective 4 – Quantitative data

We will use the quantitative data generated from objective 4 of the study to describe intervention uptake by mothers, completion of scheduled contacts with peer-supporters according to age-group and parity, recruitment and retention of peer-supporters, completeness of peer supporter diaries, follow-up of participants at 8 weeks, breastfeeding rates at initiation and at 8 weeks and other outcome measures described in Table 1, using percentages and 95% confidence intervals for categorical data and mean, standard deviation (s.d.) and 95% confidence intervals for continuous data. Thus summary data for the whole group and by site will provide information relevant to inform a full trial. The inter-class correlation will be estimated from the site data regarding variation in breast feeding outcome using ANOVA. We will describe completeness of data collected according to the different data collection methods described in appendix 1.

Objective 4 – Qualitative data

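### Peer-supporter interviews are restricted to women delivering the intervention, so recruits who leave training or do not reach the competency level are never asked why

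*Protocol*

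**What the plan says.** Section 10.2 gives the intake: "We will recruit 6-9 peer supporters (2-3 in each of the study sites) who have completed accredited BFPS training". Section 12.1 then requires a further 16 sessions (64 hours) of study training, after which they are "required to achieve fidelity scores indicating at least beginner level competency (using the MITI assessment tool) before they start their practice". It does not say what happens to a woman who does not reach that level.

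Section 14.2 defines the interview group: "We will interview all peer supporters delivering the intervention (n=6-9". Among the key topics it lists "peer supporters' training and supervision". Section 14.1(v) and the study summary (3.3) give the same number of peer-supporter interviews without the words about delivery.

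On fidelity, section 14.3 states: "We will analyse the recording of three interactions per peer supporter, covering one interaction within 48 hours after birth and two thereafter". Section 3.3 gives the total as "audio recorded peer supporter-mother contacts (n=27".

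Section 16 (Objective 4, quantitative data) lists "recruitment and retention of peer-supporters, completeness of peer supporter diaries" among the results to be described with percentages and 95% confidence intervals.

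**The concern.** Whether local women can be trained in a motivational interviewing approach and kept in the role is one of the questions this study exists to answer. Section 4.1 says that a targeted intervention will need to recruit and retain peer supporters from the recipients' own community. Section 4.2 asks whether such a programme is feasible and acceptable to develop and deliver, and part 6 of section 6 makes progression to a full trial depend on the answer.

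The interviews are the main feasibility-phase source on how the training was experienced. If only women who passed and delivered are asked, the accounts come from those for whom the training worked. Women who found it too long, too hard or incompatible with other commitments are the likeliest to explain what a full trial would meet, and they are outside the group as worded.

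The protocol does guard against this kind of selection among mothers. Section 10.5 keeps records of ineligible and non-consenting women so that differential recruitment can be detected, and section 14.2 samples mothers partly by how far they engaged. Peer supporters have no counterpart.

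**Working it through.** **Reproducing the plan's figures.** Three sites with 2 to 3 peer supporters each give 3 × 2 = 6 to 3 × 3 = 9, as section 10.2 states. Three recordings each (section 14.3) give 6 × 3 = 18 to 9 × 3 = 27. The 27 in section 3.3 is therefore the upper end: nine women practising, each supplying all three recordings.

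**Who is inside each source of evidence**, reading sections 12.1, 14.2, 14.3 and 16 together:

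| Recruit's path | Interviewed (14.2) | Recordings (14.3) | Retention figure (16) |
|---|---|---|---|
| Leaves during study training | No, never delivered | None possible | Counted, if the base is all recruited |
| Completes training, does not reach beginner level | No, never delivered | None possible | Counted, if the base is all recruited |
| Delivers, then leaves | Unclear | Not excluded | Counted |
| Delivers to the end | Yes | Yes | Counted |

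The first two rows follow from the text: section 12.1 makes the level a condition of practice, and section 14.2 makes delivery a condition of interview. The third row depends on whether *delivering* is read over the whole study or at the time of interview.

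**Size.** One woman is 1/9 = 11% to 1/6 = 17% of the group. The protocol gives no failure or attrition rate, so I assume a probability q of 10% to 40% that a recruit fails or leaves at any stage, independently of the others. The chance of at least one loss is 1 − (1 − q)^n:

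| q | n = 6 | n = 9 |
|---|---|---|
| 10% | 47% | 61% |
| 20% | 74% | 87% |
| 30% | 88% | 96% |
| 40% | 95% | 99% |

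The expected number lost is nq: 0.6 to 2.4 of six, or 0.9 to 3.6 of nine. These figures include women who leave after starting delivery. The group that is certainly excluded is smaller, and the protocol gives no basis for splitting it off.

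**Can the retention percentage stand in for interviews?** It includes leavers but is imprecise at this size. By the exact (Clopper–Pearson) method, 5 of 6 retained has a 95% interval of 36% to 99.6%, and 7 of 9 has 40% to 97%. It also gives no reasons, so explanation has to come from the interviews.

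**The case against.** The case against is substantial, and much of it stands.

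- *Retention is measured.* A reader might infer that everything learned about retention comes from women who stayed. Sections 3.3 and 16 do not support that, because retention is a planned quantitative result and counts leavers.
- *Leavers may already be included.* A woman who delivered and then left can fairly be read as within the group in section 14.2, and nothing excludes recordings she made. For her the text is unclear; it does not exclude her.
- *Fidelity concerns delivered support.* A reader might infer that the MITI scores are biased because women who did not pass supply none. They are not: a woman who never saw a mother has no interaction to score, and the competency requirement is part of the intervention. The scores mislead only if taken to show how many women can be trained to that level.
- *Equal ranges do not prove that no loss was assumed.* The range 6 to 9 can absorb loss: nine recruited and six interviewed fits every stated figure.
- *No one may fail.* Section 12.1 could be read as training to criterion. That would remove those who do not pass, but not those who leave during training.
- *Other sources exist.* The focus groups with 12 to 16 peer supporters (section 6, part 2.3) cover training needs, recruitment and retention. They inform the training and so precede it; they cannot explain why someone left it. Supervising midwives have contact at least weekly, but their account is second-hand, and the one midwife interviewed per area need not be the supervisor.
- *Detailed reporting belongs in an analysis plan.* Agreed. Step-by-step counts may be in a document not shown here, and their absence from the protocol is not a fault. The interview group is different, because the protocol itself fixes it.

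**Conclusion.** The point holds for the interview group. As worded, recruits who leave during training or do not reach beginner MITI level are not interviewed, although training is a named topic. Women who leave after starting delivery are not clearly in or out. The feasibility-phase interview evidence on training burden and reasons for leaving is therefore selected towards those who passed and delivered.

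The point does not extend to the retention percentage or to the validity of the fidelity scores for support delivered. How many women would be missing is unknown. Under the assumed 10% to 40% rate of failing or leaving, at least one loss is roughly an even chance at the low end (47% with six recruits) and close to certain at the high end (99% with nine). Each is 11% to 17% of a very small group. This is worth correcting before training starts, since a missed account from a leaver is hard to recover later.

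**What to change.** In sections 14.1(v) and 14.2, redefine the interview group as *all peer supporters who start the study training, including any who do not reach the competency level or who leave*. Approach leavers at or soon after leaving.

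In section 16 (Objective 4, quantitative data), state that retention is counted from all who start the study training. Give the number who reached beginner MITI level beside the fidelity scores, so that those scores are not taken as evidence of training success. The assessment is already required under section 12.1, so this needs no new data collection.

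The cost is mainly wording. The planned number of interviews already equals the number recruited, so interviews are added only if replacements are trained. Some leavers may decline; reporting how many were approached and how many agreed would make that visible.
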